## 12.5 Subject Course

Information regarding the subject's course such as completing the study treatment, dose delays, premature discontinuation and major protocol violation will be tabulated and summarized.

## 12.6 Correlative Laboratory Markers

Correlative biomarker endpoints are exploratory and hypothesis generating. Descriptive statistics will be applied to characterize differences within a given patient pre-treatment to post-treatment and across the cohorts of patients. Changes in the correlative endpoints will be evaluated using a two-tailed paired Student's t-test. To provide a preliminary estimate of the predictive or prognostic value of the various correlative endpoints for DFS we will be using multiple regression analysis with ordinal category for response (generalized linear models) or time to event (proportional hazards regression) as the outcome.

## 13. SAFETY REPORTING OF ADVERSE EVENTS

### 13.1 Assessment of Safety

Safety assessments will consist of monitoring and reporting adverse events (AEs) and serious adverse events (SAEs) that are considered related to THERAPY, all events of death, and any study specific issue of concern.

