### 6.2 Monitoring

Safety will be evaluated in this study through the monitoring of all serious and non-serious AEs, defined and graded according to NCI CTCAE v4.03. Patients will be assessed for safety (including laboratory values) according to the Study Calendar. Patients will be followed for safety for 30 days following the last dose of study treatment or until receipt of another anticancer therapy, whichever comes first. General safety assessments will include serial interval histories, physical examinations, and specific laboratory studies, including serum chemistries and blood counts (see Study Calendar for the list and timing of study assessments). **All serious adverse events (SAEs) will be reported in an expedited fashion.** In addition, the investigators will review and evaluate observed AEs on a regular basis.

Patients who have an ongoing study treatment–related AE upon study completion or at discontinuation from the study will be followed until the event has resolved to baseline grade, the event is assessed by the investigator as stable, new anticancer treatment is initiated, the patient is lost to follow-up, the patient withdraws consent, or until it has been determined that study treatment or participation is not the cause of the AE.

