### 8.1 Duration of Follow Up

All patients will be followed for 30 days after the last dose of treatment with the agent under this IND or until all treatment related clinical significant toxicities resolve to baseline or grade  $\leq 1$ . Adverse events with attribution of possible, probable or definite will be reported following guidelines for adverse event reporting and all SAEs will be reported for 30 days after the last dose. Patients will be followed every 3 months per standard of care for PFS and OS.

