**10.2 Safety**

Safety assessments will consist of monitoring and recording all adverse events, including serious adverse events, the monitoring of hematology, blood chemistry, coagulation parameters, urinalysis and the regular monitoring of vital signs, and physical condition as shown in corresponding tables. For details on AE collection and reporting, refer to the Safety section in the protocol.

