## **12.3 Safety**

The adverse events observed will be summarized as frequency, proportion of patients, and exact 95% confidence interval for proportion, categorized by type (organ affected or laboratory determination), severity by CTCAE v4.03 and nadir or maximum values for the laboratory measures), time of onset (i.e. course number), duration, and reversibility or outcome. Tables will be created to summarize these toxicities by dose and course.

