### 13.3 Adverse Events

An AE is any unfavorable and unintended sign, symptom, or disease temporally associated with the use of an investigational medicinal product (IMP) or other protocol-imposed intervention, regardless of attribution.

This includes the following:

- AEs not previously observed in the subject that emerge during the protocol-specified AE reporting period, including signs or symptoms associated with disease that were not present prior to the AE reporting period.
- Complications that occur as a result of protocol-mandated interventions (e.g., invasive procedures such as cardiac catheterizations).

- If applicable, AEs that occur prior to assignment of study treatment associated with medication washout, no treatment run-in, or other protocol-mandated intervention.
- Preexisting medical conditions (other than the condition being studied) judged by the investigator to have worsened in severity or frequency or changed in character during the protocol-specified AE reporting period.

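### Section 13.1 limits safety reporting to related AEs and SAEs, and section 8.1 filters non-serious AEs by attribution, while sections 6.2, 10.2 and 13.4 to 13.4.2 require all events; section 12.3 does not name the basis of the phase II primary safety tables.

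*Combined protocol and SAP*

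**What the plan says.** **Text that restricts by attribution**

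- Section 13.1 says that safety assessments are made up of "monitoring and reporting adverse events (AEs) and serious adverse events (SAEs) that are considered related to THERAPY, all events of death". The sentence then adds any study-specific issue of concern.
- Section 8.1 says: "Adverse events with attribution of possible, probable or definite will be reported following guidelines for adverse event reporting and all SAEs will be reported", with a 30-day period after the last dose. The filter here applies to non-serious AEs; SAEs are kept whatever their attribution.

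**Text that does not restrict**

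- Section 6.2: "Safety will be evaluated in this study through the monitoring of all serious and non-serious AEs".
- Section 10.2: "Safety assessments will consist of monitoring and recording all adverse events, including serious adverse events".
- Section 13.3 defines an AE by its timing in relation to an investigational product "or other protocol-imposed intervention, regardless of attribution". This is a definition; the duty to report is in the sections that follow.
- Section 13.4 makes the investigator responsible for collecting and reporting all AEs and SAEs. Section 13.4.1 applies this from first treatment until 30 days after the last administration, or until study discontinuation or termination if earlier. Section 13.4.2 has each event reported and described, with suspected relationship as one of the items recorded.
- Section 13.5.1 sends every SAE to the epacadostat supplier, whatever the suspected cause.

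**Analysis**

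Sections 1.1.2 and 3 make safety and toxicity the phase II primary endpoint. Section 12.3 says: "The adverse events observed will be summarized as frequency, proportion of patients, and exact 95% confidence interval for proportion". It lists type, severity, onset, duration and outcome as classifiers. Attribution is not among them.

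**The concern.** Sections 10.2 and 13.1 both set out what safety assessments consist of, and they give different scopes. No passage sets an order of precedence. Section 12.3 would be the natural place to settle the matter, but it names no basis, so the numerator of the phase II primary safety tables is not fixed by the text.

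Attribution is a weak filter in this trial. There is no control arm, the three components of the regimen all begin in the first week, and patients have advanced refractory disease. Section 13.4.2 allows an event to be classed as not related on evidence of underlying disease or concomitant medication. Symptoms such as fatigue and nausea, which section 2.6 lists among the common epacadostat AEs, can be attributed either way. Section 13.3 expressly counts newly emerging disease-associated signs and symptoms as AEs, whereas 13.1 would leave them out once judged unrelated.

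The two rules also differ in what they allow later. All-cause records can be cut down to treatment-related tables at any time. A related-only record cannot be expanded to include events that were never entered.

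**Working it through.** The plan states no figure on this point, so the check is a comparison of passages followed by an illustration under stated assumptions.

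**Step 1. Which events each rule admits.** Following 13.4.2, related means possibly, probably or definitely; not related means unlikely or unrelated.

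| Event | 13.1 | 8.1 | 6.2, 10.2, 13.4 to 13.4.2 | Other route |
|---|---|---|---|---|
| Non-serious, related | in | in | in | – |
| Non-serious, not related | out, unless a study-specific issue | out | in | laboratory values only: study calendar and 12.3 |
| SAE, related | in | in | in | 13.5.1 |
| SAE, not related, not fatal | out, unless a study-specific issue | in | in | 13.5.1 |
| Death | in | in, as an SAE | in | 13.5.1 |

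The rules disagree in two rows. For unrelated SAEs, 13.1 stands alone against every other passage, including 8.1, and 13.5.1 gives those events a separate route. For unrelated non-serious AEs, 13.1 and 8.1 stand together against 6.2, 10.2 and 13.4 to 13.4.2.

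**Step 2. What remains exposed.** Hematology and chemistry are scheduled for every patient (section 9.1), and 12.3 summarises nadir or maximum laboratory values, so laboratory toxicity does not depend on attribution to be recorded. That leaves non-serious, non-laboratory AEs judged unlikely or unrelated.

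**Step 3. Which results use those events.**

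- DLT and MTD (section 3, Table 10) rest mainly on treatment-related toxicity, counting anything at least possibly related. A filter at the same threshold removes little.
- Tolerability (section 6.7) rests on DLTs, on treatment-related discontinuation, and on doses missed because of toxicity.
- The Simon decision (sections 3 and 12.1) uses disease control rate.
- The AE incidence tables of 12.3 use them directly.

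**Step 4. Size, under assumptions.** The documents do not give the share of AEs that would be judged related. Let x be the number of patients with a given AE, n the cohort size and f the assumed share judged related. The reported count is f·x. The exact 95% limits are the 2.5% point of Beta(x, n−x+1) and the 97.5% point of Beta(x+1, n−x), with the reported count used as x.

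Take n = 30, the full size of cohort 1, and assume x = 12 (12/30 = 40%):

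| f | Reported | Proportion | Exact 95% CI |
|---|---|---|---|
| 1 (all-cause) | 12/30 | 40% | 22.7% to 59.4% |
| 0.75 | 9/30 | 30% | 14.7% to 49.4% |
| 0.50 | 6/30 | 20% | 7.7% to 38.6% |
| 0.25 | 3/30 | 10% | 2.1% to 26.5% |

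For cohort 2 at full size, n = 14, assume x = 6 (6/14 = 42.9%, CI 17.7% to 71.1%). With f = 0.50 this becomes 3/14 = 21.4% (CI 4.7% to 50.8%).

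In cohort 1, at f = 0.50 or below, the upper limit of the reported interval lies below the assumed all-cause 40%. The exact interval allows for sampling error only; it does not allow for a change in what is counted.

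**The case against.** The strongest reply is that the operative instructions agree with one another. Sections 13.4, 13.4.1 and 13.4.2 are the methods-and-timing text that staff would follow, and they call for all events. The AE row of the study calendar has no attribution filter, and Appendix 3 collects a form on which drug relationship is recorded. On this view 13.1 is a stray introductory sentence, and the observed events of 12.3 naturally means all of them. This stands as a forecast: all-cause collection is the likelier practice. It does not remove the contradiction. Section 13.1 is the general opening of the safety section and no rule subordinates it.

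Section 8.1 can also be read as a follow-up cross-reference, since it sits under duration of follow-up and defers to reporting guidelines. That reading is possible, but the text does not state the limit. Nor does 13.1 confine itself to expedited reporting, which has its own sections (13.5, 13.6 and 13.8).

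It is also fair that phase II safety is descriptive, with no hypothesis or threshold that could change, and that *possibly* counts as related, which is a low bar. Both points limit the consequence. Finally, making all-cause the main basis is partly a reporting preference. What the plan cannot do without is a stated basis; all-cause is proposed because it agrees with most of the protocol and still allows the related-only table.

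**Conclusion.** The contradiction is real and is in the current text. Its reach is narrow: non-serious, non-laboratory AEs judged unlikely or unrelated could be left out of the phase II primary safety tables if 13.1 is followed, and 12.3 does not say on which basis those tables are built. The size depends on the share judged related, which is unknown; the tables above show a range under assumed inputs, not an estimate.

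A reader might infer more, and the documents do not support it:

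- *That toxicity would in general be lost for good.* SAEs are reported under 13.5.1 regardless of cause, 13.1 itself keeps deaths and study-specific issues, and laboratory values are scheduled for everyone.
- *That 8.1 also drops unrelated SAEs.* It keeps all of them; only 13.1 restricts SAEs.
- *That centres would apply different rules and mix two definitions.* Section 4 describes recruitment and registration at one center. Other sections mention participating institutions, but that does not show divided practice.
- *That the background section measures the gap,* by setting AEs in all 52 subjects of one epacadostat study against treatment-related AEs in 50 of 62 (81%) in another. The first was epacadostat alone and the second was in combination with pembrolizumab, so regimen and population differ as well as attribution.

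**What to change.** 1. Reword 13.1 so that safety assessment covers all AEs and SAEs regardless of attribution, keeping its mention of deaths and study-specific issues.
2. Reword the AE sentence of 8.1 in the same way, so that it agrees with 6.2, 10.2 and 13.4 to 13.4.2.
3. In both places, have relationship recorded as an attribute of each event, as 13.4.2 already does, and not used as a condition of entry.
4. In 12.3, state that the primary safety proportions and exact intervals are all-cause, with treatment-related proportions (possible, probable or definite) also shown.

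The cost is the wording of three passages and one extra table. Data entry grows only if related-only collection would otherwise have been used. Sample size, DLT rules and the Simon boundaries do not change.

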### 13.2 Risks Associated With

Although most immune-related AEs observed with immunomodulatory agents have been mild and self-limiting, such events should be recognized early and treated promptly to avoid potential major complications.

### 13.3 Adverse Events

An AE is any unfavorable and unintended sign, symptom, or disease temporally associated with the use of an investigational medicinal product (IMP) or other protocol-imposed intervention, regardless of attribution.

This includes the following:

- AEs not previously observed in the subject that emerge during the protocol-specified AE reporting period, including signs or symptoms associated with disease that were not present prior to the AE reporting period.
- Complications that occur as a result of protocol-mandated interventions (e.g., invasive procedures such as cardiac catheterizations).

- If applicable, AEs that occur prior to assignment of study treatment associated with medication washout, no treatment run-in, or other protocol-mandated intervention.
- Preexisting medical conditions (other than the condition being studied) judged by the investigator to have worsened in severity or frequency or changed in character during the protocol-specified AE reporting period.

### **13.3.1 Serious Adverse Events**

An AE should be classified as an SAE if the following criteria are met:

- It results in death (i.e., the AE actually causes or leads to death).
- It is life threatening (i.e., the AE, in the view of the investigator, places the subject at immediate risk of death. It does not include an AE that, had it occurred in a more severe form, might have caused death.).
- It requires or prolongs inpatient hospitalization.
- It results in persistent or significant disability/incapacity (i.e., the AE results in substantial disruption of the subject's ability to conduct normal life functions).
- It results in a congenital anomaly/birth defect in a neonate/infant born to a mother exposed to the IMP.
- It is considered a significant medical event by the investigator based on medical judgment (e.g., may jeopardize the subject or may require medical/surgical intervention to prevent one of the outcomes listed above).

### **13.4 Methods and Timing for Assessing and Recording Safety Variables**

The investigator is responsible for ensuring that all AEs and SAEs that are observed or reported during the study are collected and reported to the FDA, appropriate IRB(s), Incyte, Inc. and, Dynavax, Inc. in accordance with CFR 312.32 (IND Safety Reports).

#### **13.4.1 Adverse Event Reporting Period**

The study period during which all AEs and SAEs must be reported begins at initiation of study treatment and ends 30 days following the last administration of study treatment or study discontinuation/termination, whichever is earlier. After this period, investigators should only report SAEs that are attributed to prior study treatment.

#### **13.4.2 Assessment of Adverse Events**

All AEs and SAEs whether volunteered by the subject, discovered by study personnel during questioning, or detected through physical examination, laboratory test, or other means will be reported appropriately. Each reported AE or SAE will be described by its duration (i.e., start

and end dates), regulatory seriousness criteria if applicable, suspected relationship to the therapy and radiotherapy (see following guidance), and actions taken.

To ensure consistency of AE and SAE causality assessments, investigators should apply the following general guideline:

Yes (Possibly, Probably, or Definitely)

There is a plausible temporal relationship between the onset of the AE and administration of the therapy, and the AE cannot be readily explained by the subject's clinical state, intercurrent illness, or concomitant therapies; and/or the AE follows a known pattern of response to the therapy; and/or the AE abates or resolves upon discontinuation of the therapy or dose reduction and, if applicable, reappears upon re-challenge.

No (Unlikely, Unrelated)

Evidence exists that the AE has an etiology other than the therapy (e.g., preexisting medical condition, underlying disease, intercurrent illness, or concomitant medication); and/or the AE has no plausible temporal relationship to therapy administration (e.g., cancer diagnosed 2 days after first dose of study drug).

Expected adverse events are those adverse events that are listed or characterized in the Package Insert or current Investigator Brochure.

Unexpected adverse events are those not listed in the Package Insert (P.I.) or current Investigator Brochure (I.B.) or not identified. This includes adverse events for which the specificity or severity is not consistent with the description in the P.I. or I.B. For example, under this definition, hepatic necrosis would be unexpected if the P.I. or I.B. only referred to elevated hepatic enzymes or hepatitis.

## 13.5 Procedures for SAE Reporting

### 13.5.1 Initial Reports

1. The Investigator reports to Incyte every SAE, regardless of suspected causality, which occurs after the subject has signed informed consent and up to the time that subject has completed the trial, including any post-treatment follow-up required by the protocol. Such cases are regarded as originating in the IST for the purpose of notification to Incyte.
2. The investigational site notifies Incyte of an SAE *within 24 hours* of the Investigator becoming aware of the SAE, regardless of causality to the investigational product.

The investigational site records all SAE details on the Serious Adverse Event Report Form, or on the SAE form being used by the Investigator conducting the trial, and e-mails the report to Incyte via the address: [[contact]](mailto:[contact]).

The investigational site does ***not*** provide medical records (e.g., discharge summary, relevant test results) unless requested by Incyte. Instead, the investigational site records the information relevant to the SAE on the SAE form and provides the form to Incyte.

If a non-serious AE becomes serious, the investigational site follows the process for SAE reporting.

The Incyte PhV representative, in conjunction with the Incyte PhV Service Provider, reviews the initial SAE information and determines whether the criteria for a valid case (patient ID, enrolment number, randomization number, age, sex, event, reporter name, site number, and suspect drug) are present, and assesses the report for completeness.

If necessary, the Incyte PhV representative or designee queries the investigational site (within 48 hours of receipt) for additional information to ensure a valid case prior to distributing the report for internal Incyte review.

The internal Incyte review occurs as specified in the internal Incyte SAE distribution list for IST protocols.

The report should not be delayed pending an Investigator causality assessment.

3. The Incyte PhV representative, in conjunction with the Incyte review team, ensures that all information available at the time, which is relevant to the medical/safety evaluation of the report, is collected and included without compromising the timeframes for regulatory reporting.

If only partial information is available, the report will not be delayed and must be reported to satisfy the reporting timeframe. Any additional information should be collected for a follow-up report to Health Authorities (HAs).

### 13.5.2 Follow-up Reports

1. When new information regarding the SAE, or outcome of pregnancy, becomes available, the investigational site personnel update all relevant data on the appropriate SAE Report Form, or equivalent, with any new or changed information and send the follow-up SAE report to Incyte ***within 24 hours*** of becoming aware of the new information, via e-mail to [[contact]](mailto:[contact]).

This includes any SAE that is upgraded to fatal or life-threatening.

2. Incyte's PhV Service Provider tracks any critical outstanding follow-up information and questions, and contacts the investigational site via a faxed Data Clarification Form (DCF) to request the information until all outstanding queries are resolved.

This may include requests for hospital discharge summaries, autopsy reports, death certificates (if applicable), and/or results of relevant laboratory and diagnostic tests.

After three attempts to resolve queries, which are sent at two-week intervals, the PhV Service Provider notifies the Incyte PhV representative of any outstanding queries. The Incyte PhV representative notifies the Incyte IST PM of the outstanding queries that require follow-up.

Incyte PhV will discuss with the Incyte IST PM action plans for non-responsive sites (e.g., certified letter, site visit), as needed.

3. The investigational site faxes the DCF response to the PhV Service Provider, using the fax number provided on the Fax transmission sheet from the PhV Service Provider.
4. The PhV Service Provider appends to the case, in the safety database, all additional documentation submitted by the site and generated during follow-up SAE collection, including the Incyte internal SAE questions and/or copies of the amended SAE reports.

